4.3.2 Dosage, Administration, and Compliance

4.3.2.1 MHAA4549A and Placebo

The randomization of patients will be managed by a central IxRS. All patients will be randomly assigned to receive either a single dose of MHAA4549A 3600 mg IV or placebo IV at a 1:1 ratio. Oseltamivir will be dispensed via IxRS. Oseltamivir dosing is described in [Table 2](#).

Administration of MHAA4549A or placebo will be performed in a setting with emergency medical equipment and personnel who are trained to monitor for and respond to medical emergencies. A qualified physician will be on site during study drug administration for all patients.

A single dose of MHAA4549A or placebo will be delivered by IV infusion following dilution in 0.9% normal saline over approximately 60 minutes. Study drug should be delivered using a 0.22 µm in-line filter. Compatibility testing has shown that MHAA4549A is stable when diluted in 0.9% normal saline in a polyvinylchloride, polyolefin bag, or ethylene vinyl acetate bag (EVA), at or above a combined total concentration of 0.24 mg/mL up to 27.0 mg/mL. Study drug must be administered within the treatment window outlined in [Section 3.1.1](#). Further detailed instructions for preparation of study drug can be found in the Pharmacy Manual.

There are no recommended dosage modifications for MHAA4549A since it is a single infusion. Any overdose or incorrect administration of study drug should be noted on the Study Drug Administration electronic Case Report Form (eCRF). Adverse events associated with an overdose or incorrect administration of study drug should be recorded on the Adverse Event eCRF. General supportive measures will be taken to manage any AEs associated with overdose. Patients experiencing such AEs will be followed up clinically until the event has resolved.

Trained clinical site staff responsible for adequate and accurate study drug administration, accounting, and management will administer study drugs to patients. Study drug preparation and dosing instructions will be provided to each site. The exact times of study drug administration will be recorded in the relevant dispensing/administration logs and patient's source notes. Any noncompliance or problems with study drug administration will be recorded in the patient's source notes and reported to the Sponsor if appropriate.

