5.2.3 Non-Serious Adverse Events of Special Interest (Immediately Reportable to the Sponsor)

Non-serious adverse events of special interest (AESI) are required to be reported by the investigator to the Sponsor immediately (i.e., no more than 24 hours after learning of the event; see [Section 5.4.2](#) for reporting instructions). Adverse events of special interest for this study include the following:

- Cases of potential drug-induced liver injury that include an elevated ALT or AST in combination with either an elevated bilirubin or clinical jaundice, as defined by Hy's law (see [Section 5.3.5.6](#))
- Suspected transmission of an infectious agent by the study drug, as defined below
 - Any organism, virus, or infectious particle (e.g., prion protein transmitting transmissible spongiform encephalopathy), pathogenic or non-pathogenic, is considered an infectious agent. A transmission of an infectious agent may be suspected from clinical symptoms or laboratory findings that indicate an infection in a patient exposed to a medicinal product. This term applies only when a contamination of the study drug is suspected.

- Adverse events associated with suspected cases of infusion-related reactions (IRR) which occur within 24 hours of study drug administration and may show the following signs and symptoms (for guidance on reporting AEs associated with IRR, see [Section 5.3.5.1](#) below):
 - Fever and/or shaking chills
 - Flushing and/or itching
 - Alterations in heart rate and blood pressure
 - Dyspnea or chest discomfort
 - Back or abdominal pain
 - Nausea, vomiting, and/or diarrhea
 - Various types of skin rashes
 - Anaphylaxis
- Anaphylaxis due to IV drugs most often presents with the following signs and symptoms:
 - Cutaneous symptoms: flushing, itching, urticaria, and/or angioedema (usually of face, eyelids, or lips)
 - Respiratory symptoms: repetitive cough, sudden nasal congestion, shortness of breath, chest tightness, wheeze, sensation of throat closure or choking, and or change in voice quality due to laryngeal edema
 - Cardiovascular symptoms: faintness, tachycardia (or less often bradycardia), tunnel vision, chest pain, hypotension, sense of impending doom, and/or loss of consciousness
 - Gastrointestinal symptoms: such as nausea, vomiting, abdominal cramping, and diarrhea

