6.3 SUMMARIES OF TREATMENT GROUP COMPARABILITY

Demographic and baseline characteristics of the patient will be summarized for all randomized patients by treatment group by use of descriptive statistics. Baseline is defined as the last available value prior to study drug administration.

During the study; patient disposition, concurrent treatment, and compliance with study treatment and visits will be summarized on the safety analysis population using descriptive statistics.

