6.5 SAFETY ANALYSES

The safety analyses will include all randomized patients who received study drug, with patients grouped according to the treatment actually received. Safety parameters to be evaluated include adverse events (including deaths, serious adverse events, discontinuations due to adverse events, and the incidence and severity of adverse events), clinical laboratory tests, vital signs (including SpO₂ measurements), and ECGs.

All collected adverse event data will be listed by study site and patient number. All adverse events that occur on or after treatment on Day 1 will be summarized for each treatment group by mapped term, appropriate thesaurus levels, body system, and event within each body system, and toxicity grade. In addition, all serious adverse events, including deaths, will be listed separately and summarized. SAEs caused by a protocol-mandated intervention (e.g., invasive procedures such as biopsies, discontinuation of medications) that occur between consent and first dose of study medication will be listed separately.

Laboratory data with values outside of the normal ranges will be identified. In addition, select laboratory data will be summarized by treatment group using descriptive summary statistics.

The absolute and percentage changes from baseline in vital sign parameters will be computed, and changes deemed clinically significant by the Investigator will be noted. Appropriate descriptive summary statistics will be provided for all vital sign parameters

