APPENDIX 1a Schedule of Assessments: Hospitalization Days

Notes: Unless otherwise indicated, all assessments on Day 1 should be performed prior to study drug administration; x's within parentheses, i.e., (x), indicate optional assessments. Please refer to Follow-up Period table for visits to be completed after patient is discharged from hospital prior to Day 60.

Day (D)	Screening	Hospitalized Days (only to be completed while patients are hospitalized)														Hospital Discharge ^a	D30	D60 Study Completion or Early Discontinuation while Hospitalized
	D -2,-1	D1 (Randomization)	D2	D3	D4	D5	D6	D7	D8	D9	D10	D14	D20	D25				
Confirm study drug administration can occur within 48 hours of hospital admission																		
Informed consent ^b	x																	
Rapid influenza A test ^c	x																	
Local influenza A PCR test ^d	x																	
Inclusion/exclusion criteria	x																	
Medical history and demographic data	x																	
Confirm onset of flu symptoms (≤ 5 days prior to study drug administration on Day 1)	x																	
Confirm history of baseline SpO ₂ > 92%	x																	
Pregnancy screening ^e	x																	
Confirm O ₂ requirement ^f	x																	
Respiratory Assessment ^g	x	x	x	x	x	x	x	x	x	x	x	x	x	x	x	x	x	
Concomitant medications ^h	x	x	x	x	x	x	x	x	x	x	x	x	x	x	x	x	x	
Vital signs ⁱ		x	x	x	x	x	x	x	x	x	x	x	x	x	x	x	x	
APACHE score ^j		(x ^z)										(x)			(x)	(x)	(x)	
SOFA score ^k		(x ^z)						(x)				(x)			(x)	(x)	(x)	
Electrocardiogram (12-lead) ^l		x				x						x			x	x	x	
Randomization		x																

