- ^h Concomitant medications should be recorded for 30 days prior to screening, through the study completion/early discontinuation visit. See exclusion criteria in [Section 4.5.2](#) for prohibited therapies.
- ⁱ Vital signs will be collected within 1 hour before MHAA4549A infusion and within 1 hour after completion of MHAA4549A infusion include temperature, respiratory rate, heart rate, systolic blood pressure, and diastolic blood pressure. Temperature should be measured using the same methodology throughout the study and should be measured prior to administration of any antipyretic drugs. In patients who have multiple vital signs taken during any day, the most abnormal value should be recorded from that 24-hour period. Temperature, blood pressure, respiratory rate, and heart rate will be completed after the patient has been supine for > 5 minutes. The worst/most abnormal value from the last 24-hour period should be recorded for patients who are in the ICU.
- ^j APACHE scores are optional and only for patients that are in the ICU. For calculation of the screening APACHE score, the worst values in the preceding 24 hours should be used. APACHE scores are not required for study conduct or entry but should be collected if available.
- ^k SOFA scores are only for patients in the ICU that have available data such as PaO₂/FiO₂ (mmHg). See Appendix 7 for SOFA score calculation.
- ^l Patient should rest in a supine position for 10 minutes prior.
- ^m Patient will be a resident for at least 24 hours following administration of MHAA4549A.
- ⁿ Oseltamivir must be given for a minimum of 5 days. Treatment longer than 5 days is permitted based on the discretion of the investigator [indicated by (x)].

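### The most-abnormal-value rule in Appendix 1a has no Day 1 exception, so followed as written it can displace the pre-infusion vital-sign baseline that Sections 6.3 and 6.5 rely on

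*Combined protocol and SAP*

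**What the plan says.** Footnote i to the Appendix 1a schedule (Version 3, VHP Only) opens with two timed collections: "Vital signs will be collected within 1 hour before MHAA4549A infusion and within 1 hour after completion of MHAA4549A infusion". Section 4.3.2.1 gives the length of the infusion: "A single dose of MHAA4549A or placebo will be delivered by IV infusion following dilution in 0.9% normal saline over approximately 60 minutes".

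The same footnote then sets a recording rule: "In patients who have multiple vital signs taken during any day, the most abnormal value should be recorded from that 24-hour period". A further sentence covers intensive care: "The worst/most abnormal value from the last 24-hour period should be recorded for patients who are in the ICU". The two timed collections and the daily rule also stand in the initial protocol and in Version 2. The ICU sentence stands in Versions 2 and 3.

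The note at the head of the schedule reads "Unless otherwise indicated, all assessments on Day 1 should be performed prior to study drug administration", and footnote i is such an indication for vital signs. The vital-signs row has its first entry on Day 1 and none at screening.

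On the analysis side, Section 6.3 states "Baseline is defined as the last available value prior to study drug administration" and Section 6.5 states "The absolute and percentage changes from baseline in vital sign parameters will be computed". Section 5.2.3 lists "Alterations in heart rate and blood pressure" among the signs of a suspected infusion-related reaction.

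**The concern.** The rule applies to any day with more than one reading, and on Day 1 the protocol itself requires two. Read literally, it therefore reaches every dosed patient and leaves one value per parameter. That value may be the post-infusion one. In the ICU it may also come from hours before dosing. Neither is reliably the last value before study drug.

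Elsewhere the schedule is explicit when it wants more than one value or a time kept. Footnote g asks for both the on-oxygen and the off-oxygen SpO2, and footnote v asks for the exact draw time of PK samples. Footnote i asks for neither. Sites (about 170 are planned) are left to decide how the two rules fit together.

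Two things are at stake. The first is the baseline for every vital-sign change table. The second is the pre-to-post-infusion comparison around the only antibody dose in the trial. If the antibody disturbs vital signs during infusion, the disturbance would be partly absorbed into the active arm's baseline, and the return to normal would then read as benefit.

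**Working it through.** The plan gives no figure for this point, so there is nothing to reproduce. The check sets the passages side by side and then illustrates the size.

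**1. Do the two sets fall under the daily rule?** The longest gap is 1 h before + about 60 min infusion + 1 h after = about 3 h. They will normally lie in one 24-hour period, so the rule covers both.

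**2. Does the recorded value meet the baseline definition?**
- Section 6.3 needs the last pre-dose value.
- The daily rule gives the worse of pre-dose and post-dose, together with any other reading that day.
- The ICU rule gives the worst of 24 hours, which need not be the last value or close to dosing.
- The vital-signs row has no screening entry, so there is no earlier scheduled set of temperature, respiratory rate, heart rate or blood pressure to fall back on.

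So the rule and the definition disagree unless the worst value happens to be the last pre-dose one.

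**3. Shift with no infusion effect.** Take a parameter for which higher is worse, two normal readings with common SD, and within-patient correlation ρ. The documents give neither SD nor ρ; I assume ρ from 0.5 to 0.9 and work in SD units. The expected excess of the worse reading over the pre-dose mean is √((1−ρ)/π):
- ρ = 0.5: √(0.5/π) = 0.40 SD
- ρ = 0.7: √(0.3/π) = 0.31 SD
- ρ = 0.9: √(0.1/π) = 0.18 SD

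The recorded value is then post-dose in 50% of patients. This shift is the same in both arms.

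**4. Shift with an infusion effect in the active arm only.** Assume an effect d = 0.5 SD. The post-minus-pre difference has mean d and SD θ = √(2(1−ρ)). The mean shift is d·Φ(d/θ) + θ·φ(d/θ), and the share of recorded values that are post-dose is Φ(d/θ).

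| ρ | θ | Φ(d/θ) | Active-arm shift (SD) | Shift without effect (SD) | Excess in active arm (SD) | Excess ÷ 0.5 |
|---|---|---|---|---|---|---|
| 0.5 | 1.000 | 69% | 0.346 + 0.352 = 0.70 | 0.40 | 0.30 | 60% |
| 0.7 | 0.775 | 74% | 0.370 + 0.251 = 0.62 | 0.31 | 0.31 | 62% |
| 0.9 | 0.447 | 87% | 0.434 + 0.096 = 0.53 | 0.18 | 0.35 | 70% |

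A simulation with two million patients per setting agrees (0.697, 0.622 and 0.530 SD).

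**5. Reading the last two columns.** The between-arm difference in the recorded Day 1 value is 0.30 to 0.35 SD instead of 0.5, so the infusion signal is weakened. If that value is used as baseline, change from baseline at later visits favours the active arm by the same 0.30 to 0.35 SD even when the arms are equal at those visits.

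**6. ICU.** I give no figure for the worst-of-24-hours rule, because the number and correlation of readings are not in the documents. Section 3.2.2 reports that 27% of the source population needed ICU admission, so the group is not negligible.

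**The case against.** The strongest reply is that the collapse is not shown. Footnote i specifies two sets tied to the infusion, and Section 6.3 presupposes a pre-dose value. The daily rule could be meant only for additional ward or ICU readings, and it does not say that only the worst value is kept. Section 4.6.6 refers to eCRF instructions for ICU vital signs, and an eCRF with separate pre-infusion and post-infusion fields is equally possible. This stands: the eCRF is not supplied, so the consequence is conditional.

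A reader might infer more: that the pre-dose readings are lost in every patient, and that any infusion effect smaller than the expected-maximum offset is undetectable. With independent readings that offset is 0.56 SD for the worse of two and about 1.95 SD for the worst of 24. The documents do not support this. They do not say how the sets are entered. Readings at most about 3 h apart in one patient are unlikely to be independent, and 24 hourly ICU readings are nowhere specified. An expected offset is also not a detection limit. Both arms receive an infusion under the same rule, so the common part cancels between arms, and 60% to 70% of the assumed effect survives even on the literal reading.

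It is also true that infusion reactions have their own route: immediate reporting under Section 5.2.3 and recording as individual signs under Section 5.3.5.1. That covers clinically significant reactions. It does not replace the paired readings. Under Section 5.3.5.5 an abnormal vital sign must be reported only if it is symptomatic, changes treatment, leads to an intervention or other therapy, or is judged clinically significant. A systematic asymptomatic shift need not appear.

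**Conclusion.** The point holds as a conflict between a stated recording rule and the stated baseline definition. If footnote i is followed as written, the Day 1 vital-sign value can be post-dose or a 24-hour extreme, and no earlier scheduled set can replace it.

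The illustrative size is a baseline shift of 0.18 to 0.40 SD common to both arms, plus 0.30 to 0.35 SD in the active arm under a 0.5 SD infusion effect. These figures rest on assumed correlation, normality, effect size and a parameter for which higher is worse. For blood pressure, where either direction can be abnormal, the pattern would be less simple.

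The reach is limited to the vital-sign safety summaries and the Day 1 vital-sign values. The primary endpoint uses the separate respiratory assessment in footnote g and is unaffected. No sample-size or power figure changes. Version 5 (Global) is announced with an additional 8400 mg arm, but its body is not supplied, so whether the wording persists there cannot be checked.

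**What to change.** - In Appendix 1a, footnote i, state that on Day 1 the pre-infusion and post-infusion sets are each recorded with clock time, and that neither the most-abnormal-value rule nor the ICU 24-hour rule applies to them. Any ICU 24-hour worst value on Day 1 goes in a separate field.
- In Section 6.5, state that the timed pre-infusion set is the vital-sign baseline, consistent with Section 6.3, and add a table of pre-to-post-infusion change by arm.
- Check that the Version 5 schedule and the eCRF completion instructions carry the same wording.

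The cost is a sentence or two in the footnote, one in Section 6.5, one more table and, if the eCRF does not already have it, one extra timed Day 1 entry. Both sets are already measured, so nothing is added for patients.

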APPENDIX 1a (cont'd)

Schedule of Assessments: Hospitalization Days

- ^o Complete physical examination includes evaluations of general appearance of head, eye, ear, nose, and throat, cardiovascular, dermatological, musculoskeletal, respiratory, gastrointestinal, genitourinary, and neurological systems. Changes from any prior examination should be recorded. New or worsened abnormalities should be recorded as adverse events, if appropriate.
- ^p Limited, symptom-directed physical examination includes, at a minimum, evaluation of general appearance, dermatological examination of the injection sites, evaluations directed by patient-reported symptoms, and any other evaluations that the investigator deems clinically relevant. Changes from any prior examination should be recorded. New or worsened abnormalities should be recorded as adverse events, if appropriate.
- ^q Height will be obtained at screening only. Weight will be obtained at all indicated visits. Height and weight will be recorded in centimeters and kilograms, respectively.
- ^r Local laboratory measurements should be utilized.
- ^s Urinalysis includes pH, specific gravity, glucose, protein, ketones, blood, bilirubin, nitrite, and leukocyte esterase. Microscopic examination (e.g., sediment, RBCs, WBCs, casts, crystals, epithelial cells, bacteria) will be performed if clinically indicated.
- ^t [REDACTED]
- ^v Day 1 serum PK samples are to be drawn 30 (\pm 5) minutes pre-dose of MHAA4549A, 60 (\pm 15) minutes after the end of infusion. PK samples will be drawn from the contralateral arm from that used for drug infusion and must be labeled with the exact time of draw.
- ^w [REDACTED]
- ^x If patient is discharged on or before Day 5, the oseltamivir PK sample should be taken on the discharge day.
- ^y [REDACTED]
- ^z Assessment to be conducted based on entry into ICU; may vary from patient to patient.
- ^{aa} For optional thyroid stimulating hormone test.
- ^{bb} HIV serology result not needed for randomization.
- ^{cc} Patients who are discharged from the hospital with oseltamivir will be required to complete a medication diary and return the medication diary, empty (used) oseltamivir packets and unused oseltamivir capsules to the study site at the next follow up visit. Patients will record the date and time when each oseltamivir capsule is administered.

APPENDIX 1b Schedule of Assessments: Follow-Up Period

- If a patient is discharged prior to Day 14, he/she will need to complete the following assessments for Day 14, Day 30, and Day 60 below.
- If a patient is discharged prior to Day 30 and after Day 14, he/she will need to complete the following assessments for Day 30 and Day 60 below.
- If a patient is discharged prior to Day 60 but after Day 30, he/she will need to complete the following assessments for Day 60 below.
- If patient is hospitalized for Day 14, Day 30, and/or Day 60, please refer to Appendix 1a.

Day (D)	D14 ± 1 (If discharged BEFORE D14)	D30 ± 4 (If discharged BEFORE D30)	Day 60 ± 4 (Study Completion) or Early Discontinuation
Concomitant medications ^a	x	x	x
Vital signs ^b	x	x	x
Electrocardiogram (12-lead) ^c	x	x	x
Weight & height, BMI ^d	x	x	x
Adverse events	x	x	x
Hematology ^e	x	x	x
Chemistry panel ^e	x	x	x
Coagulation panel ^e	x	x	x
Urinalysis ^e	x	x	x
Flu antibodies (HAI)	x	x	x
████████████████████		x	x
Serum for MHAA4549A PK measurements ^f	x	x	x
████████████████████	x	x	x
████████████████████	x	x	x
██████████		x	x
██████████		x	x
██████████		x	x
██████████		x	x

██████████; ATA = Anti-therapeutic antibodies; BMI = body mass index; D = day; Dx = diagnostics; eCFR = electronic Case Report Form; ECG = electrocardiogram; HAI = hemagglutinin inhibition; ██████████; PD = pharmacodynamics; PK = pharmacokinetic.

^a Concomitant medications should be recorded for 30 days prior to screening, through the study completion/early discontinuation visit. See exclusion criteria in [Section 4.5.2](#) for prohibited therapies.

APPENDIX 1b (cont'd) Schedule of Assessments: Follow-up Period

- ^b Vital signs include temperature, respiratory rate, heart rate, systolic blood pressure, and diastolic blood pressure. Temperature should be measured using the same methodology throughout the study and should be measured prior to study drug administration of any antipyretic drugs. In patients who have multiple vital signs taken during any day, the most abnormal value should be recorded from that 24-hour period. Temperature, blood pressure, respiratory rate, and heart rate will be completed after the patient has been supine for > 5 minutes.
- ^c ECG should be recorded after the patient has rested in a supine position for 10 minutes.
- ^d Height will be obtained at screening only. Weight will be obtained at all indicated visits. Height and weight will be recorded in meters and kg, respectively.
- ^e Local laboratory measurements should be used.
- ^f PK samples should be drawn from the opposite arm from the one used for drug infusion and must be labeled with the exact time of draw.

APPENDIX 2

Time to Normalization of Respiratory Function

For the purposes of this study, the time to normalization of respiratory function will be defined as the time to removal of the patient from O₂ supplementation in order to maintain an SpO₂ > 95%.

Patients who are on low flow O₂ (2-6L/min) should receive a daily trial off O₂ in the morning between 6 am – 12 pm as described below.

1. Patient should be resting or sitting.
2. Patient should be fitted with pulse oximeter, and their SpO₂ should be checked once while on O₂ and then again 3 – 5 minutes after turning off O₂ supplementation.
3. If the SpO₂ > 95%, then the time and reading should be recorded. Notify the study doctor so that he/she can make a clinical judgment to determine whether the O₂ can be removed.
4. If the patient is off O₂ for 24 hours and his/her reading the subsequent day is >95%, then the endpoint is considered satisfied. The recorded time for the endpoint corresponds with the initial discontinuation of O₂ and reading.

APPENDIX 3

[REDACTED]

[REDACTED]

[REDACTED]

[REDACTED]

APPENDIX 4

[REDACTED]

[REDACTED]

[REDACTED]

[REDACTED]

[REDACTED]

[REDACTED]

[REDACTED]

[REDACTED]

APPENDIX 5

[Redacted]

[Redacted]
[Redacted]
[Redacted]

[Redacted]
[Redacted]

[Redacted]
[Redacted]

[Redacted]

[Redacted] [Redacted]
[Redacted]

[Redacted] [Redacted]

[Redacted] [Redacted]
[Redacted]

[Redacted] [Redacted]
[Redacted]

[Redacted]

[Redacted]

[Redacted]

[Redacted]

[Redacted]

APPENDIX 6

[REDACTED]

[REDACTED]

[REDACTED]

[REDACTED]

[REDACTED]

APPENDIX 7

SOFA Score Calculation

Administration of MHAA4549A will be performed in a setting with emergency medical equipment and personnel who are trained to monitor for and respond to medical emergencies. A qualified physician will be on site during study drug administration for all patients.

The following equipment is needed in the event of a suspected anaphylactic reaction during study drug infusion:

- Airway management equipment
- O₂
- Epinephrine for subcutaneous, intravenous, and/or endotracheal use in accordance with standard practice
- Antihistamines
- Corticosteroids
- IV infusion solutions, tubing, catheters, and tape

The following are the procedures to follow in the event of a suspected anaphylactic reaction during study drug infusion:

Stop the study drug infusion.

Maintain an adequate airway.

Administer antihistamines, epinephrine, or other medications as required by patient status and directed by the physician in charge.

Continue to observe the patient and document observations.

APPENDIX 8
DAIDS Toxicity Grading Tables for Clinical Abnormalities

**From the FDA Guidance document ‘Toxicity Grading Scale for
Healthy Adult and Adolescent Volunteers Enrolled in
Preventative Vaccine Clinical Trials’ (September 2007)**

Vital Signs ^a	Mild (Grade 1)	Moderate (Grade 2)	Severe (Grade 3)	Potentially Life Threatening (Grade 4)
Fever (°C) ^b (°F)*	38.0 – 38.4 100.4 – 101.1	38.5 – 38.9 101.2 – 102.0	39.0 – 40.0 102.1 – 104.0	>40 >104
Tachycardia – beats per minute	101- 115	116 – 130	>130	ER visit or hospitalization for arrhythmia
Bradycardia – beats per minute ^c	50 – 54	45 – 49	<45	ER visit or hospitalization for arrhythmia
Hypertension (systolic) – mmHg	141 – 150	151 – 155	>155	ER visit or hospitalization for malignant hypertension
Hypertension (diastolic) – mmHg	91 – 95	96 – 100	>100	ER visit or hospitalization for malignant hypertension
Hypotension (systolic) – mmHg	85 – 89	80 – 84	<80	ER visit or hospitalization for hypotensive shock
Respiratory Rate – breaths per minute	17 – 20	21 – 25	>25	Intubation

^a Subject should be at rest for all vital sign measurements.

^b Oral/tympanic temperature; no recent hot or cold beverages or smoking.

^c When resting heart rate is between 60 – 100 beats per minute. Use clinical judgment when characterizing bradycardia among some healthy subject populations, for example, conditioned athletes.

